We hypothesize that combining both strategies (daily drainage with the addition of talc sclerosant) will lead to both earlier, and higher incidence of pleurodesis in the majority of treated patients. We believe that this can be achieved on an outpatient basis without additional interactions with the healthcare system.

Design and Procedures

To assess if the addition of talc sclerosant to daily outpatient drainage compared with daily drainage alone leads to more rapid pleurodesis.

Study Type: Non-blinded prospective randomized two-arm cohort

Primary Endpoint: Proportion of cohort able to have TPC removed at 30 days post talc-administration (day of randomization will be defined as study day 1)

Secondary Endpoints: Quality-of-Life Assessment, dyspnea assessment, adverse events

Schedule of Events:

	Screening (up to 14 days prior to baseline visit)	Baseline (Day 0)	30 day follow-up visit	60 day follow-up visit
Tunnel Pleural Catheter insertion (SOC*)	X			
Chest x-ray (SOC)	X		X	X
Physical Exam (SOC)	X	X	X	X
Randomization		X		
Talc instillation (if randomized to Talc Arm) (SOC)		X		
Vital sign monitoring for 2 hours post Talc instillation (if randomized to Talc Arm) (SOC)		X		
SOB VAS questionnaire		X	X	X
SF-36 questionnaire		X	X	X
Daily drainage diary review		X	X	X
AE review		X	X	X

*Standard of Care (SOC) procedures

Enrollment

Patients will undergo TPC insertion for malignant pleural effusion as per usual clinical indications and protocols in either the inpatient or outpatient setting. Patients will be eligible for study enrollment anytime between catheter insertion and initial clinical follow-up at a maximum of 14 days following TPC insertion. Patients will be instructed to drain that catheter daily until initial follow-up. At this 7-14 day follow-up appointment for suture removal patients will be asked to drain the morning of the clinic visit and a chest x-ray (CXR) will be performed prior to the clinic visit. The catheter may be drained at the time of the clinic visit if not done within 8 hours of the visit. Patients who meet radiographic criteria for inclusion (see inclusion/exclusion criteria below) may proceed with randomization via central computer generated randomization table. Those who do not meet radiographic criteria will be considered screen

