Pleurodesis is defined as three consecutive drainage attempts with 50cc or less or less than 200cc in 1 week. Patients will be instructed to contact their treatment team who will obtain a CXR to evaluate for resolution of effusion. A CXR showing effusion \leq the size of the effusion at randomization will be considered to be successful pleurodesis. Chest x-ray imaging showing an effusion larger than what was present at randomization (radiographic score 2-5) will be investigated for dysfunction of the pleural catheter. Thoracic ultrasound will be performed at the time of removal of each catheter to assess for presence and size of residual pleural fluid, pleural septations, and for the presence or absence of lung sliding (appendix 1).

Management of Dysfunctional Catheters

Obstructed catheters will be investigated per ASAP I protocol by instillation of 2mg TPA in 8ml sterile water and allowed to dwell for 20 minutes followed by drainage. If the output returns to $>200cc$

after fibrinolytic infusion then patient will return to study protocol. If fibrinolytic fails to produce immediate drainage and the patient does not have shortness of breath the catheter will be removed and the patient will be considered to have undergone partial response. Patients with continued shortness of breath will be managed at the discretion of the treating physician and will be considered catheter failures.

Outcome Measures

Primary Outcome: Percentage of cohort undergoing accelerated pleurodesis. Patients able to have their TPC removed at 30 days post-talc instillation will be considered to have achieved the primary endpoint. Pleurodesis is defined as three consecutive drainage attempts with 50cc or less or less than 200cc in 7 days and lack of respiratory symptoms of cough or shortness of breath previously attributed to pleural effusion. Patients will be considered to have experienced complete (CR) or partial response (PR) depending on chest x-ray (CXR) scoring criteria. Patients who experience pleurodesis later than 30 days from randomization will be considered to have a delayed CR or PR using the same CXR scoring criteria.

Chest X-ray scoring (see appendix 1): Chest x-ray scoring will be performed by a blinded pulmonologist viewing images identified with study code on a CD supplied by the treating physician. Patients with CR will have a CXR score of 0-1, and PR ≥ 2 .

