8. Subject or caregiver is able to perform home drainage of the pleural effusion (a caregiver can be a friend, family member, or paid healthcare professional).

Exclusion Criteria:

Potential study subjects will be excluded if 1 or more of the following exclusion criteria is present:

1. Subject has significant trapped lung, or a proximal bronchial obstruction which is likely to lead to trapped lung. For a subject to be eligible for this study, two separate study center clinicians must agree that there is no significant trapped lung on the same CXR using visual estimation (reference guide). The CXR used to make this decision must have been performed ≤ 30 days preceding the consent form being signed, and must have been performed preferably on the same day, but no more than 7 calendar days after tunneled pleural catheter insertion.

Significant trapped lung is deemed present if any 1 of the following criteria is met:

- a) A CXR shows hydropneumothorax other than small (< 1 cm between chest wall and pleural line) apical pneumothoraces.
- b) A CXR shows $\geq 20\%$ of the affected hemithorax to be free of the expected lung parenchymal markings and there is no suggestion of pleural fluid.
- c) A CXR shows $\geq 20\%$ of the affected hemithorax to be occupied with pleural fluid AFTER a pleural aspiration which resulted in symptoms suggestive of trapped lung (e.g., chest pain or cough).
2. Subject has a Karnofsky score < 50 , or a World Health Organization (WHO)/Eastern Cooperative Oncology Group (ECOG) performance status ≥ 3 . Subjects who have a performance status of 3 may be considered for the study if the removal of their fluid would likely improve their performance score by 1 or more.
3. Subject is pregnant, planning to become pregnant, or is lactating.
4. Subject has a history of empyema.
5. Subject has a history of chylothorax.
6. Subject has an uncorrected coagulopathy.

Randomization and Allocation

Randomization will be performed utilizing a computer system at Duke (the coordinating center) with permuted block randomization of random block length. Allocation will occur at the time of initial clinic visit following catheter insertion.

Data Collection

Data will be collected using paper clinical research forms at the clinical sites followed by direct entry into a web based, password protected REDCAP database. Duplicate databases will be stored on Duke and VA servers to safeguard data security.

Initial Data Collection

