Data to be collected at the time of enrollment include age, sex, race, ethnicity, effusion side, type of malignancy, date of diagnosis, date of initial thoracentesis, Karnofsky performance score, ECOG performance score, comorbidities (anemia, asthma, cerebrovascular accident, chronic kidney disease, chronic obstructive pulmonary disease, coagulopathy, congestive heart failure, coronary artery disease, diabetes, deep vein thrombosis, pulmonary embolism, hypertension, hypothyroidism, hyperthyroidism, interstitial lung disease, nephrotic syndrome, peripheral vascular disease, cirrhosis of the liver), pleural fluid characteristics (pH, LDH, Protein, % lymphocytes, glucose, cytology results), prior chemotherapy, prior radiotherapy, prior immunomodulatory therapy, VAS dyspnea score, and SF-36 questionnaire. Data collected at randomization will be CXR score by treating and blinded physician.

Follow-up Data Collection

Karnofsky score, ECOG score, VAS dyspnea score, SF-36 questionnaire, and CXR scoring will be collected at the 30 day and 90 day clinic visits, or at the time of catheter removal. Thoracic ultrasound examination will be performed at time of catheter removal.

Subject Recruitment and Compensation

Consent Process- Consent form and material subject to IRB approval

Risk/benefit assessment- There are two primary risks to patients associated with this study. The first is the risk of respiratory failure associated with talc pleurodesis. Respiratory failure is a rare but well documented risk associated with the use of talc for pleurodesis. This event is rarely fatal and occurs roughly 1 in every 10,000 patients when utilizing graded talc. The second concern is obstruction of the tunneled pleural catheter by talc. This happens spontaneously in about 10% of patients and can be managed in >90% of these patients with the instillation of tissue plasminogen activator through the catheter. Previous trials of talc instillation through tunneled pleural catheters have not noted a higher than baseline rate of TPC blockage with this treatment regimen. Expected side effects of talc instillation include pain and fever which are temporary and can be treated with over the counter analgesics and anti-pyretics.

Potential benefits of participation in this study include less long-term fluid collection and potential earlier removal of the catheter.

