Cost to the Subject- There will be no increased cost of care to the patients as the instillation will occur during routine follow up visit after TPC placement. Talc will be supplied as part of clinical care. Clinic visits are occurring as part of our routine clinical care for malignant pleural effusion treated with tunneled pleural catheters. Drainage bottles will be obtained through usual care pathways.

Data Analysis and Statistics

Power Calculation

Assuming a 45% rate of TPC removal in the control arm, and a 65% rate of TPC removal in the experimental arm (a 20% improvement) and a margin of error of 5% we calculate we would need to enroll 92 patients per group to have 90% power to detect a significant difference with $p<0.05$ using a one sided superiority test. Given a 10% dropout rate seen in the other two major studies within this field, we assume we would need 101 patient's per treatment arm. We anticipate including 2 centers in this study and we estimate that accrual will be reached within 36 months. Study will be completed at 40 months to allow for complete follow up of all patients enrolled.

[figure not shown]
Statistics will be performed by a statistician blinded to which treatment group allocation

Planned Interim Analysis

An interim analysis will be conducted once 100 subjects have been recruited and 90 day data collected. Analysis will be for the primary outcome only. Statistically significant difference in pleurodesis rates as measured by Fisher's Exact Test with $p < 0.05$ will trigger early termination of the study.

Data and Safety Monitoring

All study records will be kept securely by in the study coordinators or local site investigators office. Digital records will utilize secured Redcap database software on the Duke or VA networks. Only the study personnel will have access to the records. Subject data will be coded with a study number after recruitment. The code crosswalk key will be kept in a separate location from the study data.

References

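### No stratification factor or covariate is named; adjusting the primary comparison for site and baseline chest X-ray score would be a small, inexpensive gain

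*Combined protocol and SAP*

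**What the plan says.** - **Allocation.** The Enrollment section says that patients who meet the radiographic criteria "may proceed with randomization via central computer generated randomization table". Randomization and Allocation adds that the coordinating center's system uses "permuted block randomization of random block length". Neither section names a stratification factor.
- **Sites.** Power Calculation states: "We anticipate including 2 centers in this study". The title page lists a university medical center and a VA medical center.
- **Primary endpoint.** "Proportion of cohort able to have TPC removed at 30 days post talc-administration" (Design and Procedures).
- **Baseline CXR score.** Initial Data Collection states: "Data collected at randomization will be CXR score by treating and blinded physician". Criteria for Pleurodesis uses the baseline film as the reference: an effusion no larger than "the size of the effusion at randomization will be considered to be successful pleurodesis".
- **Analysis.** Planned Interim Analysis sets early termination on "Statistically significant difference in pleurodesis rates as measured by Fisher's Exact Test" at p < 0.05. Power Calculation refers only to a one-sided superiority test. No section describes the final comparison of arms, and none mentions a site term or a covariate.

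**The concern.** Site could plausibly affect the endpoint. The trial is open-label, patients report to their own treating team, and management of some catheter problems is left to the treating physician. Baseline effusion size could also matter, because success is judged against it. If either predicts removal, a comparison that ignores it carries avoidable noise, and a chance imbalance between arms moves the estimate. Both variables are already available, so using them needs no new data. What is at stake is some precision and some protection against an awkward baseline table in a trial of about 200 patients.

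**Working it through.** **The plan's own figure.** Inputs from Power Calculation: 45% removal in the control arm, 65% in the talc arm, one-sided 0.05, 90% power, 92 per group, 101 after dropout. With unpooled variance:

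n = (1.645 + 1.282)² × (0.45×0.55 + 0.65×0.35) / 0.20² = 8.564 × 0.475 / 0.04 = 101.7, so 102 per group.

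The pooled formula gives 105. The stated 92 is not reproduced. At 92 per group, one-sided power is 87.3% (unpooled), 86.5% (pooled) or 82.2% (exact Fisher). That is a separate point; here it only sets the starting power.

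**Assumptions.** The documents do not give the site split or the outcome gap between sites. I take a smaller-site share q of 10-50% and a gap D in removal rates of 5-30 points, the same in both arms. The results apply to any two-level baseline factor.

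**Chance imbalance without stratification, 101 per arm.** SD of the between-arm difference in site share = √(2q(1−q)/101).

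- q = 30%: √(0.42/101) = 6.4 points, so a 95% range of about ±12.6 points.
- Simulated permuted blocks (sizes 2, 4 and 6 assumed): SD 4.2 points at q = 10%, rising to 7.1 at q = 50%. The chance of an imbalance above 10 points is 1.3% (q = 10%), 6.7% (20%), 10.8% (30%) and 14.1% (50%).
- The resulting shift in the risk difference is D times the imbalance. A 10-point imbalance moves it by 0.5 points (D = 5) to 3.0 points (D = 30), against a target of 20.

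**Relation to the standard error.** SE of the risk difference at 101 per arm = √(0.475/101) = 6.9 points. The shift is one component of this SE and does not add to it.

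**Variance removed by adjustment.** The share is [2q(1−q)D²/n] / [0.475/n] = q(1−q)D²/0.2375. Sample size cancels, so the share is the same at the interim look.

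| Smaller-site share | D = 5 | D = 10 | D = 20 | D = 30 |
|---|---|---|---|---|
| 10% | 0.1% | 0.4% | 1.5% | 3.4% |
| 30% | 0.2% | 0.9% | 3.5% | 8.0% |
| 50% | 0.3% | 1.1% | 4.2% | 9.5% |

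**Effect on power, 92 per arm, one-sided 0.05.** The unadjusted SE is √(0.475/92) = 7.19 points, and 20/7.19 − 1.645 = 1.138 gives 87.3%. With 4.2% of the variance removed, power is 88.5%, the most for any gap up to 20 points. With 9.5% removed, it is 90.0%.

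**Simulation check.** Runs of 8,000 trials at 92 per arm (q 20-50%, D 10-30 points) compared an unadjusted z test with a site-stratified Cochran-Mantel-Haenszel test. The stratified test gained about 0.5 to 3.5 points of power (Monte Carlo SE about 0.4 points on each power figure). One-sided type I error was 3.7-5.0% for the unadjusted test and 4.8-5.6% for the stratified test. The logistic model itself was not simulated.

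**CXR score.** The documents do not say how strongly it predicts removal, so no figure can be attached to it.

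**The case against.** The case against is substantial, and most of it stands as a limit on size.

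- A reader might infer that the plan fixes an unadjusted Fisher's test as its final primary analysis. It does not: that test is tied to the interim look, and no final analysis is given. The point is therefore that no specified analysis uses these variables. Likewise, the documents are silent on stratification; they do not state that the list is unstratified.
- A reader might infer that an unstratified list biases the result or inflates false positives. It does neither. Randomization makes the unadjusted comparison unbiased on average, and the simulated type I error stayed at or below about 5%. Each site's team decides on removal in both arms, so a site effect alone does not favor talc. If knowledge of the arm influences removal, adjusting for site would not correct that.
- The larger gains need a site gap equal to or above the 20-point treatment effect. Both sites apply the same numeric drainage criteria, so a small gap is plausible, and a gap of 10 points or less yields at most about 1% of variance.
- The CXR argument is the weaker half. Complete and partial response, which the score separates, both count as pleurodesis. Radiographic eligibility and the earlier days of drainage may narrow the range of baseline scores. The blinded score is read from a disc supplied by the treating physician and may not be ready at allocation. This argues against stratifying on it, but leaves it usable as a covariate.
- Site-specific blocks in an open-label trial are somewhat easier to guess than one list shared by two sites. Random block lengths reduce this without removing it.

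None of these points makes a prespecified adjusted comparison harmful or expensive.

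**Conclusion.** The point holds as a minor improvement. Site and the baseline blinded CXR score are both available, and no planned analysis uses either. For site, the benefit is about 0.1-9.5% of variance and about 0 to 3 points of power. It rests on assumed shares of 10-50% and gaps of 5-30 points, and the lower part of that range is as credible as the upper. For the CXR score, a benefit is plausible but unquantified. A reader might hope that adjustment restores the stated 90% power. In the unpooled calculation that happens only at the extreme corner (50% share, 30-point gap), so the sample size has to be dealt with separately.

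**What to change.** Add the missing description of the final primary analysis. Compare 30-day catheter removal between arms by logistic regression with terms for treatment, site and baseline blinded CXR score, and report a standardized risk difference with its confidence interval. State that the blinded reading is the one used, how the score enters the model, and what is done if a reading is missing. Keep the unadjusted test as supportive. A site-stratified Mantel-Haenszel test is a simpler alternative, but it does not use the CXR score.

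If the randomization system allows it, also stratify the central list by site (two strata) and keep random block lengths. The CXR score is better left as a covariate.

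The cost is a short passage of analysis text and, optionally, one system setting, with no extra patients or data. The downsides are a slightly more complex primary model and, if the list is stratified, slightly more predictable allocation within a site.

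### With 92 patients per group, power for 45% versus 65% at one-sided 0.05 is about 86–87%, not the stated 90%

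*Combined protocol and SAP*

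**What the plan says.** All the inputs are in the Power Calculation paragraph of Data Analysis and Statistics.

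- **Rates:** "Assuming a 45% rate of TPC removal in the control arm" and "a 65% rate of TPC removal in the experimental arm (a 20% improvement").
- **Test:** significance at p<0.05, "using a one sided superiority test". The same sentence also gives "a margin of error of 5" per cent, without saying what that is.
- **Result:** "we calculate we would need to enroll 92 patients per group to have 90% power to detect a significant difference".
- **Dropout:** 10%, taken from two earlier studies, after which "we assume we would need 101 patient's per treatment arm".

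The readable text names neither the formula or software behind 92 nor the test for the final analysis. The only test named is in Planned Interim Analysis, where a difference "as measured by Fisher's Exact Test" with p<0.05 stops the trial. A figure in this section is not reproduced in the copy reviewed.

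**The concern.** Two proportions, a one-sided alpha and a power fix the sample size to within a few patients, whichever standard formula is used. For a 20-point difference near 50%, 92 per group looks too small for 90% power at one-sided 0.05. The inflation to 101 also looks like multiplication by 1.10 rather than division by 0.90.

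This is the only power statement in the plan, and the enrolment target rests on it. It tells readers that a true 45% versus 65% benefit would be missed one time in ten. If the real risk is higher, a null result would be read as stronger evidence against that benefit than the design supports.

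**Working it through.** **Inputs** (all from the Power Calculation paragraph): p₁ = 0.45, p₂ = 0.65, difference 0.20, one-sided alpha 0.05 (z = 1.645), power 90% (z = 1.2816), equal groups, dropout 10%.

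Variance terms:
- Unpooled: 0.45×0.55 + 0.65×0.35 = 0.2475 + 0.2275 = 0.475
- Pooled: 2×0.55×0.45 = 0.495

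**Step 1. Try to reproduce 92.**
- Unpooled: n = (1.645 + 1.2816)² × 0.475 / 0.20² = 101.7, so 102.
- Pooled: n = [1.645×√0.495 + 1.2816×√0.475]² / 0.20² = 104.1, so 105.

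Other methods and readings, per group:

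| Setting | n per group |
|---|---|
| Arcsine, one-sided 0.05, 90% | 105 |
| Log odds ratio, one-sided 0.05, 90% | 108 |
| Pooled with continuity correction, one-sided 0.05, 90% | 114 |
| Pooled, two-sided 0.05, 90% | 128 |
| 5% read as a superiority margin, one-sided 0.05, 90% | 181 |
| 5% read as a non-inferiority margin, one-sided 0.05, 90% | 66 |
| Unpooled, two-sided 0.05, 80% | 93.2, so 94 |

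The plan's 92 is not reproduced. The closest of these readings, the last row, contradicts both the stated power and the stated one-sided test, and still does not give 92.

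**Step 2. Power at the stated sizes** (single look, one-sided 0.05).

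Pooled power = Φ[(0.20×√n − 1.645×√0.495)/√0.475]. At n = 92 this is Φ[(1.918 − 1.157)/0.689] = Φ(1.104) = 86.5%.

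Unpooled power = Φ[0.20×√n/√0.475 − 1.645].

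| n per arm | Pooled | Unpooled | Pooled z test, exact binomial | One-sided Fisher, exact |
|---|---|---|---|---|
| 91 | 86.2% | 86.9% | 85.9% | 82.1% |
| 92 | 86.5% | 87.3% | 85.7% | 82.2% |
| 101 | 89.2% | 89.8% | 89.5% | 86.7% |
| 105 | 90.2% | 90.8% | 91.0% | 88.5% |

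The Fisher column is a sensitivity check only, because the plan names that test for the interim and not for the final analysis.

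**Step 3. Dropout.**
- 92×1.10 = 101.2, which matches the stated 101.
- Keeping 92 after a 10% loss: 92/0.90 = 102.2, so 103.
- Expected evaluable from 101: 101×0.90 = 90.9, about 91, with pooled power 86.2% and a miss risk of 13.8%.
- For 90% power: 105/0.90 = 116.7, so 117 enrolled per arm (pooled); 102/0.90 = 113.3, so 114 (unpooled).

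**Step 4. What 91 per arm can detect.** With the control rate at 45%, pooled power reaches 90% at an experimental rate of 66.3%, a difference of 21.3 points.

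**Step 5. Does the interim look make up the shortfall?** Exact two-stage power was computed for Fisher's test at p<0.05 at the interim, then the pooled z test at 91 per arm.

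| Evaluable per arm at interim | Two-sided Fisher | One-sided Fisher |
|---|---|---|
| 50 | 86.5% | 87.0% |
| 45 | 86.4% | 87.3% |

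It does not. These figures use an unadjusted 0.05 at both looks, so any gain over the single-look figure comes with added type I error.

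**The case against.** Several points can fairly be made for the plan.

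- **The dropout slip is tiny.** Multiplying by 1.10 is a common shortcut. Here it costs two enrolled patients, or about one evaluable patient, per arm, and moves pooled power only from 86.5% to 86.2%. This stands: it is a side note, and the main error is the 92.
- **The 91 evaluable is conditional.** The endpoint is worded as a proportion of the cohort, and nothing says outright that dropouts leave the denominator. If all 101 per arm contributed outcomes at the assumed rates, power would be 89.2% to 89.8%, close to the claim. But inflating for dropout only makes sense if dropouts are lost to the analysis, so 91 is the plan's own implied number. Nor does this rescue the statement about 92.
- **105 is one approximation.** The unpooled formula gives 102, and exact enumeration of the pooled z test gives 89.9% at 102 and 90.3% at 103. This stands: the requirement is best given as a range of about 102 to 105.
- **No final test is named in the readable text.** Any restated power therefore supplies one. This also stands. The figure must be tied to a named test, since a one-sided Fisher test would bring it to about 82%.
- **The missing figure may show other settings, or define the 5%.** Its content is unknown, so nothing is held against the plan for it. If its settings differ, text and figure disagree and the sentence still needs correcting.

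**Conclusion.** The concern holds. On the printed inputs, 92 per group gives about 86.5% power (pooled) or 87.3% (unpooled), not 90%. No standard setting tried that keeps the stated alpha, one-sided test and power yields 92. The shortfall is 10 to 13 evaluable patients per group (102 − 92 and 105 − 92). At the planned 101 per arm with 10% lost, the single-look miss risk is about 14% rather than 10%.

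This assumes the stated 45% and 65%, 1:1 allocation, dropouts excluded from the analysis, and a pooled z test at the end. The error is modest and does not threaten the design, but the plan claims a power it does not have, so the statement should be fixed. The undefined 5% is a minor wording matter: it may simply restate alpha, and none of the readings tried explains 92.

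**What to change.** Keep enrolment at 101 per arm and rewrite the paragraph.

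1. Name the final test first, and state the formula or software used for the power figure.
2. If the final test is the pooled z test, wording such as this would serve:

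> Randomising 101 per arm, with 10% dropout, leaves about 91 evaluable per arm. This gives about 86% power to detect 45% versus 65% at one-sided 0.05 (pooled z test, normal approximation, single look). Power of 90% would need 105 evaluable, or 117 enrolled, per arm.

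3. If another test is intended, recompute for that test. The unpooled formula gives 86.9% at 91 per arm and needs 102 evaluable, or 114 enrolled, for 90%. A one-sided Fisher test gives about 82% at 91.
4. Inflate for dropout by dividing by 0.90.
5. Define the 5% margin of error, or delete it if it only repeats alpha.

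The cost is protocol wording only. Enrolment is unchanged, and the stated power falls by about 3 to 4 points.

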**Randomized Controlled Trial of Talc Instillation In Addition To Daily Drainage
Through a Tunneled Pleural Catheter to Improve Rates of Outpatient
Pleurodesis in Patients with Malignant Pleural Effusion – The ASAP II Trial**

Participating Sites:

Duke University Medical Center

Durham VA Medical Center

NCT04792970

Version Date: 01/01/2021

Purpose of the Study

To assess the efficacy of talc instilled via tunneled pleural catheter combined with daily drainage to induce accelerated pleurodesis in patients with malignant pleural effusion. *Our hypothesis is that the combination of talc instillation with daily drainage will increase rates of pleurodesis compared with daily drainage alone.*

Background and Significance

Tunneled Pleural Catheters (TPC's) are an increasingly utilized for the management of malignant pleural effusions (MPEs). TPCs provide rapid relief of dyspnea and improvement in quality-of-life in patients with MPEs.^{1,2} Spontaneous pleurodesis may occur through repetitive drainage of the pleural space, however the rates and timing of this event are variable and have been reported to be between 16% and 65%.^{1,3,4} Earlier pleurodesis leads to lower supply costs and reduced risk of long term complications such as infection, pain or mechanical failure.^{5,6} This is especially important as malignant pleural effusion is associated with a generally poor prognosis and if given limited life expectancy, minimizing medical interference and hospitalized days is paramount.^{7,8}

Recent advances in the field of malignant pleural effusion management have prioritized these patient centered goals of maximizing quality of life improvements while minimizing time in the hospital. Recent research by our own group has shown a 20% improvement in the percentage of patients having their TPC removed by 12 weeks with high volume daily drainage of pleural effusions at home.⁹ Parallel research has demonstrated that the addition of talc through a TPC achieves a similar 20% improvement in pleurodesis within the first 5 weeks.¹⁰ Somewhat surprisingly, the rates of pleurodesis were nearly identical between the 2 studies at 48% and 43% respectively^{9,10}. Notably, patients in the talc study drained their effusions using an every other day or symptom guided strategy rather than daily drainage.

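### The 10% dropout inflation does not fit an endpoint defined on the whole cohort, and no rule says how death, withdrawal or loss before day 30 is counted

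*Combined protocol and SAP*

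**What the plan says.** Under Data Analysis and Statistics, Power Calculation, the plan assumes TPC removal of 45% in the control arm and 65% in the talc arm. It asks for 92 patients per group "to have 90% power" at p<0.05, "using a one sided superiority test". It then raises the number to 101 per arm with the words "Given a 10% dropout rate seen in the other two major studies within this field".

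Under Design and Procedures the primary endpoint is "Proportion of cohort able to have TPC removed at 30 days post talc-administration". Outcome Measures likewise expresses the primary outcome as a percentage of the cohort.

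The protocol provides for complete, partial and delayed response, and for catheter failure when a catheter is obstructed. It has no category for a patient who dies, withdraws or is lost before day 30 with the catheter in place. It names no analysis population and no missing-data method. Fisher's exact test is specified for the interim analysis, but no test is named for the final one.

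Background and Significance notes that "malignant pleural effusion is associated with a generally poor prognosis". It reports pleurodesis rates of 48% and 43% from the two earlier studies without their denominators.

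**The concern.** Inflating for dropout is the right adjustment when dropouts contribute no outcome. With a whole-cohort endpoint, a patient who leaves with the catheter in place does contribute one: not achieved. The sizing therefore implies one denominator and the endpoint wording another, and nothing in the plan chooses between them.

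The choice matters in this setting. The protocol itself describes a poor prognosis, so some deaths before day 30 are foreseeable. At the plan's own 10%, about 20 of 202 patients (0.10 × 202 = 20.2) would be classified without a written rule, in a trial where patients and treating clinicians know the allocation. Leaving them out conditions the comparison on something that happens after randomization. Keeping them in as non-success preserves the randomized comparison, but it can shrink the difference that the trial was sized to detect.

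**Working it through.** **Inputs.** From the Power Calculation: p1 = 0.45, p2 = 0.65, one-sided α = 0.05 (the plan's 5% margin of error is read as α), power 90%, 92 per arm, 10% dropout, 101 per arm. Assumed here: 1:1 allocation (implied by equal group sizes), a pooled-variance z-test for the final comparison, and all loss occurring by day 30.

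**Formulas.** With Δ = p2 − p1, p̄ = (p1 + p2)/2, s0 = √[2p̄(1 − p̄)] and s1 = √[p1(1 − p1) + p2(1 − p2)]:

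- n per arm = (1.645·s0 + 1.282·s1)² / Δ²
- power = Φ[(Δ√n − 1.645·s0) / s1]

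**Step 1: the plan's own figures.** Here s0 = √(2 × 0.55 × 0.45) = 0.7036 and s1 = √(0.2475 + 0.2275) = 0.6892.

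- Required n = (1.157 + 0.883)² / 0.04 ≈ 104.1, so 105 per arm. The stated 92 is not reproduced. An unpooled variance gives 102 and a continuity correction 114.
- Power at 92 per arm: Φ[(0.20 × 9.592 − 1.157)/0.6892] = Φ(1.104) = 86.5%, before any dropout.
- The 101 is 92 × 1.1 = 101.2. Dividing instead, 92/0.9 = 102.2, gives 103; this difference is minor.

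**Step 2: power at 101 randomized per arm under each reading of the denominator.**

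| Reading | Rates | n analysed per arm | Power |
|---|---|---|---|
| 10% excluded | 45% vs 65% | 101 × 0.9 = 90.9 | Φ(1.088) ≈ 86% |
| 10% kept as non-success; 45%/65% are completer rates | 0.45 × 0.9 = 40.5% vs 0.65 × 0.9 = 58.5% | 101 | Φ(0.929) ≈ 82% |
| 45%/65% are already whole-cohort rates | 45% vs 65% | 101 | Φ(1.237) ≈ 89% |

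For the second row, other assumed loss rates give:

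- 5% loss (42.75% vs 61.75%): 86% power
- 15% loss (38.25% vs 55.25%): 78% power

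To reach 90%, the second reading at 10% loss would need 131 per arm and the third would need 105.

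**Step 3: bias if dropouts are left out.** Assume no true difference, with 40.5% of all randomized patients succeeding in each arm and every lost patient a non-success. The observed rate is then 0.405/(1 − loss).

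- Loss 10% in both arms: 0.405/0.90 = 45.0% in each, so no false difference.
- Loss 10% control, 15% talc: 45.0% vs 0.405/0.85 = 47.6%, a false gain of 2.6 points.
- Loss 10% control, 20% talc: 45.0% vs 0.405/0.80 = 50.6%, a false gain of 5.6 points.

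The unequal losses are illustrations; the documents give no loss by arm.

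**The case against.** The strongest reply is that the plan never says dropouts are excluded. That is correct: exclusion is inferred from the inflation alone. The endpoint wording, read literally, already makes a patient who dies with the catheter in place a non-success. On that reading the inflation is merely the wrong adjustment, not evidence of a completer analysis. What remains is that the two passages point different ways and no rule settles the matter.

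A reader might infer that the result must be either biased or underpowered because of dropout. The documents do not support that.

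- Completer analysis gives no false difference under the null when loss is equal in the two arms and lost patients are non-successes.
- If 45% and 65% are whole-cohort rates, analysing everyone involves no exclusion and gives about 89%, close to the target. The denominators are not stated, so this cannot be ruled out.
- The whole gap from 90% to 82% should not be charged to dropout. The stated 92 gives 86.5% with no loss at all, which is a separate sizing error. With completer rates, moving from exclusion to non-success costs about 4 points (86% to 82%).
- The 10% comes from two other studies and has no time frame attached. Placing all of it before day 30 is an assumption, and no day-30 death rate is given.

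A reader might also point to respiratory failure after talc as the cause of unequal loss. The Risk/benefit assessment puts it at roughly 1 in 10,000, or about 0.01 expected events in 101 talc patients (101/10,000), so it cannot produce a 5-point excess. Withdrawal influenced by known allocation is the more plausible route.

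**Conclusion.** The point holds as an inconsistency and an omission. The inflation and the endpoint imply different denominators, and the plan does not say how death, withdrawal or loss before day 30 enters the primary analysis. At 101 per arm the power is about 82%, 86% or 89% depending on the reading, so the unwritten rule moves it by about 7 points and no reading gives the stated 90%. These figures rest on a one-sided 0.05 z-test and, for the first two, on a 10% loss complete by day 30. The 82% additionally requires 45% and 65% to be completer rates. Bias under a completer analysis is a possibility that depends on loss differing by arm, not an established result.

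**What to change.** - State that the primary analysis includes all randomized patients in their assigned arm, and that death, withdrawal or loss by day 30 without meeting the endpoint counts as not achieved.
- Report the evaluable-only result and a best/worst-case analysis as sensitivity analyses.
- State whether 45% and 65% are whole-cohort or completer rates.
- Restate the power at 101 per arm on that basis: about 89% if whole-cohort, or about 82% if completer rates with 10% loss. Correct the claim that 92 per arm gives 90%.

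The cost is a few lines of text, two sensitivity analyses and a less favourable stated power. No additional patients are needed unless the sponsor wishes to keep 90%.
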